6.1.4 Accountability for Study Drug

Subjects will be instructed to bring all study medication in the original container at each clinic visit for drug accountability. The Investigator will be responsible for maintaining accurate records for all study drug bottles dispensed and tablets returned. The inventory and dispensing logs must be available for inspection. Study medication supplies, including partially used or empty bottles, must be accounted for by the study staff prior to destruction of return.

The Investigator is responsible for ensuring adequate accountability of all used and unused study drug. This included acknowledgement of receipt of each shipment of study drug (quality and condition). All used and unused study drug dispensed to subjects must be returned to the site.

Study Drug accountability records will:

- Date received and quantity of IP kits
- Date, subject number, subject initials, the IP kit number dispensed
- Date, quantity of used and unused IP returned, along with the initials of the person recording the information

6.1.5 Product Return or Disposal

Study drug return or disposal will be performed on site. Unopened drugs that were not dispensed will be returned to Gilead.

6.2 Study Procedure

The study procedures to be conducted for each subject enrolled are as follows (also in table form in appendix 2).

6.2.1 Subject Enrollment

It is the responsibility of the Investigator to ensure that subjects are eligible for study prior to their enrollment.

6.2.2 Assessments

6.2.2.1 Screening Visit

Subjects will be screened within 30 days before Day 1 to determine eligibility for participation in the study. The following will be performed and documented at screening:

- Obtain written informed consent(s)
- Obtain medical history, including history of HIV-1 disease related events and current medications as well as any medications within 30 days of the screening visit
- If available, obtain documentation of historical genotype(s) and Hepatitis B immunity.
- Obtain measurements of blood pressure, pulse, temperature, height and weight
- Complete physical exam (genital/rectal exam, if clinically indicated)
- Obtain blood and urine samples as described in section 6.2.9
- Record all AE/SAE's to any protocol mandated procedures occurring after signing of the consent form

Subjects meeting all inclusion criteria and no exclusion criteria will return to the clinic within 30 days for the Day 1Visit. Subjects must continue their current HAART up until their scheduled Day 1 Visit

6.2.2.2 Day 1/Baseline Visit

The Investigator must have confirmed eligibility before proceeding with the Day 1 Visit.

The subject must complete prior to being administered the study drug:

- Subject will read PRO questionnaires (appendix 3) and write/mark answers directly onto questionnaire.
- Review/record SAE/AE's and changes in concomitant medications
- Obtain measurements of blood pressure, pulse, temperature, height and weight
- Complete physical exam (genital/rectal exam, if clinically indicated)
- Obtain blood and urine samples as described in section 6.2.9
- Dispense study drug
- Observe first dose administration of study drug.
- Subjects will be counseled regarding the importance of adherence and taking the study medication at the same time each day.
- Record all AE/SAE's to any protocol mandated procedures

6.2.2.3 Treatment Assessments (Week 4-48)

The following evaluations are to be completed at Weeks 4, 8, 12, 24, 36, and 48.

Study visits are to be completed within ± 2 days of the protocol specified visit date (based on the Day 1 visit) through Week 12, visits for Week 12, 24, 36 and 48 should be completed ± 6 days of the protocol specified date. If the subject is not evaluated within the visit window, the database will reflect missing/no available data for that visit.

Regularly scheduled evaluations will be made on all the subjects, even if they no longer are receiving study drug.

The following will be completed at each visit:

- Subject will read PRO questionnaires (appendix 3) to themselves and write/mark answers directly onto questionnaire.
- Review/record of SAE/AE's and changes in concomitant medications

- Obtain measurements of blood pressure, pulse, temperature, height and weight
- Complete or symptom directed physical exam, as clinically indicated
- Subjects will be reminded of the importance of adherence and taking the study medication at the same time each day
- Obtain blood and urine samples as described in section 6.2.4.1
- Document dispensing of study drug and accountability for all study drugs.
- Subjects should be reminded of the importance of adherence and taking the study medication at the same time each day.
- Record all AE/SAE's to any protocol mandated procedures
- Subjects who meet criteria for virologic failure will be managed according to the Management of Virologic Rebound Section 6.2.5.

A prescription will be provided for continuation of antiviral therapy at the final study appointment. The subject will receive an additional 7 day supply of the study drug to prevent lapse in therapy.

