8.2 Analysis Conventions

8.2.1 Analysis Sets

8.2.2 Full Analysis Set

The primary analysis set for efficacy analyses is defined as FAS, which will include all subjects who have received at least 1 dose of study drug. Subjects who do not receive at least 1 dose of study drug will be excluded from all analysis.

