8.3 Data Handling Conventions

For analysis purposes, laboratory data that are continuous in nature but are ≤ the lower limit or ≥ the upper limit of quantitation will be inputted to the value of the lower limit minus 1 or upper limit plus 1 significant digit, respectively (e.g., If HIV-1 RNA results of 'No HIV-1 RNA detected' and '≤ 50 copies/mL HIV-1 RNA detected' will be inputted as 49 copies/mL).

Missing data can have an impact upon the interpretation of the trial data. In general, values for missing data from the specified visit will not be inputted. However, a missing pre-treatment laboratory result would be treated as normal (i.e. No toxicity grade) for the laboratory abnormality summary.

All available data for subjects that do not complete the study will be included in data listings.

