8.5.1.1 US FDA-defined Snapshot Algorithm

All HIV-1 RNA data collected on-treatment (i.e. including data collected up to 1 day after the last dose date of the study drug) will be used in the snapshot algorithm. Virologic outcome will be defined as the following categories:

- HIV-1 RNA < 50 copies/mL: subjects who meet this criteria by result of the last available ontreatment laboratory result in the Week 48 analysis window
- HIV-1 RNA ≥ 50 copies/mL: subjects who meet this criteria by result of the last available ontreatment laboratory result in the Week 48 analysis window or do not have laboratory results in the Week 48 window and who discontinue study drug either:
 - due to lack of efficacy or
 - for reason other than lack of efficacy and have the last available on-treatment HIV-1 RNA ≥ 50 copies/mL
- No virologic Data in the Week 48 Analysis Window: subjects who do not have on-treatment HIV-1 RNA data in the Week 48 window because
 - Discontinuation of the study drug for reason other than lack of efficacy and have the last available on-treatment HIV-1 RNA < 50 copies/mL or
 - Missing data during the Week 48 window but remain on study drug

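### The Week 48 window is ±6 days in one place, ±6 weeks in another and undefined in the snapshot rule, so some on-drug results could be counted or dropped

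*Combined protocol and SAP*

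**What the plan says.** Three places in the combined protocol and SAP bear on the window.

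- **Section 6.2.2.3** sets the visit timing: "visits for Week 12, 24, 36 and 48 should be completed ± 6 days of the protocol specified date". It then gives the consequence of missing it: "If the subject is not evaluated within the visit window, the database will reflect missing/no available data for that visit".
- **Appendix 1** marks Weeks 12, 24 and 36 with footnote b (±6 days) and gives the Week 48 column a mark of its own. The third footnote, between b and the hepatitis B note, reads ±6 weeks.
- **Section 8.5.1.1** begins from "All HIV-1 RNA data collected on-treatment (i.e. including data collected up to 1 day after the last dose date of the study drug" and says these data feed the snapshot algorithm. The <50 category contains "subjects who meet this criteria by result of the last available ontreatment laboratory result in the Week 48 analysis window", and the ≥50 category uses the same window. One route into the no-virologic-data category is "Missing data during the Week 48 window but remain on study drug". No day limits for this window appear here or elsewhere in the document.

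Two further rules fix what happens next. The Full Analysis Set (8.2.2) is the population "which will include all subjects who have received at least 1 dose of study drug", so the denominator does not shrink when a result is dropped. Section 8.3 adds: "In general, values for missing data from the specified visit will not be inputted".

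**The concern.** The primary endpoint (≥50 copies/mL) and the first secondary endpoint (<50 copies/mL) are both read from the Week 48 analysis window. If an analyst takes the window from Appendix 1, a result obtained five weeks early counts. If the database follows Section 6.2.2.3, that visit is recorded as having no data, and the subject is classed as missing although a valid on-treatment measurement exists. Section 8.5.1.1's statement that all on-treatment data are used points the other way, and nothing says which rule governs.

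For subjects measured between the two limits, dropping the result can only lower both proportions, because the denominator stays at all dosed subjects. In a single cohort with no comparator and no test, these two proportions are the main result. An undefined window also leaves room to choose it after the data have been seen.

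**Working it through.** The plan states no power calculation, failure rate or off-window rate, so there is no figure to reproduce. The check is window arithmetic, followed by an illustration with assumed rates.

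**Inputs from the documents.** Week 48 visit at ±6 days (6.2.2.3); Week 48 at ±6 weeks (Appendix 1); about 100 subjects (4.3 and 8.8); all dosed subjects in the denominator (8.2.2).

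**Window arithmetic.**
- Week 48 = 48 × 7 = day 336.
- ±6 days: days 330 to 342, which is 13 days.
- ±6 weeks (±42 days): days 294 to 378, which is 85 days.
- Disagreement: 85 − 13 = 72 days, namely 294–329 (36 days) and 343–378 (36 days). If Week 48 is numbered day 337 instead, every limit moves by one day and the 72 is unchanged.

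**Classification of one subject.** The subject is on study drug and the only Week 48 result falls on a disputed day.

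| Reading | Result ≥50 | Result <50 |
|---|---|---|
| 8.5.1.1 with the Appendix 1 window | failure | success |
| 6.2.2.3 rule applied | no virologic data | no virologic data |

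At N = 100 each such subject moves one outcome by 1 percentage point.

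**Illustration (assumed rates).** Let p be the true failure rate and l the share of subjects tested between the limits, independent of outcome. With N = 100:
- ≥50: 100p if counted, 100p(1 − l) if dropped; fall = 100pl.
- <50: 100(1 − p) if counted, 100(1 − p)(1 − l) if dropped; fall = 100(1 − p)l.

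| p | l | ≥50: counted → dropped | <50: counted → dropped |
|---|---|---|---|
| 2% | 10% | 2.0 → 1.8 | 98.0 → 88.2 |
| 1% | 5% | 1.0 → 0.95 | 99.0 → 94.05 |
| 5% | 5% | 5.0 → 4.75 | 95.0 → 90.25 |
| 1% | 30% | 1.0 → 0.7 | 99.0 → 69.3 |
| 5% | 30% | 5.0 → 3.5 | 95.0 → 66.5 |

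In the first row 10 subjects move to no virologic data. Over p from 1% to 5% and l from 5% to 30%, the ≥50 count falls by 0.05 to 1.5 subjects and the <50 proportion by 4.75 to 29.7 points.

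**Chance that at least one of m true failures is lost** = 1 − (1 − l)^m:
- m = 2, l = 10%: 1 − 0.9² = 0.19.
- m = 1, l = 5%: 0.05.
- m = 5, l = 30%: 1 − 0.7⁵ = 0.83.

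**The case against.** **The ±6 weeks may be a slip for days.** The footnote's letter is lost in the extracted text and it directly follows a ±6 days note. The link to Week 48 is nonetheless secure by elimination: notes a and b belong to other visits and the later notes to hepatitis tests. Whether weeks was intended cannot be settled from the documents. If it is a slip, the two visit windows agree, but the snapshot window still has no limits and the missing-data rule still conflicts with using all on-treatment results.

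**The snapshot algorithm is an external definition that may carry its own limits.** Possibly, but the plan writes the algorithm out and leaves the limits off. The Section 6.2.2.3 rule also acts earlier, on what the database holds.

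**Section 6.2.2.3 concerns visit conduct, and 8.5.1.1 is the specific analysis rule.** This is a fair reading, and it means the loss of results is not certain. No sentence gives 8.5.1.1 precedence.

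**Few subjects may fall on the 72 days.** This has some force. An early result requires attendance at least 7 days ahead of schedule. On the late side, the schedule shows no dispensing between Week 36 and the final visit. If three 30-tablet bottles were given at Week 36 (an assumption), 90 tablets cover the 84 days to Week 48 plus about 6. A sample taken more than 1 day after the last dose is not on-treatment under either window.

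**The size reflects the assumptions.** This is also true: the fall in the <50 proportion is close to the assumed between-limit share, and the 0.83 combines two extremes. The effect on the primary is small beside its sampling error; the exact 95% interval for 2 of 100 is 0.2% to 7.0%. Some subjects who discontinue count as ≥50 without any result in the window, so the split is confined to those still on drug.

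**Conclusion.** The concern holds. The plan gives two different Week 48 windows, leaves the one that determines the primary endpoint without limits, and contains a database rule that, followed as written, would turn real on-treatment measurements into missing data. The 72 disputed days and the shift of 1 percentage point per affected subject follow from the documents, taking N = 100 and the third footnote as Week 48's. How many subjects would be affected is unknown, so the 98.0 versus 88.2 and 2.0 versus 1.8 figures are illustrations only. The effect falls mainly on the <50 proportion; the primary changes only when a between-limit result is ≥50. Because the analysis is descriptive, no inferential conclusion flips. It should be fixed before analysis, since two analysts following different sections could report different headline figures.

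**What to change.** Reconcile Section 6.2.2.3, Section 8.5.1.1 and Appendix 1 before the data are analysed:

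1. State one Week 48 analysis window in 8.5.1.1, in study days. Appendix 1 already prints ±6 weeks; if that is not what was meant, correct it and give the intended limits.
2. Keep ±6 days in 6.2.2.3 as the scheduling target only.
3. Replace the missing-data sentence in 6.2.2.3 with a statement that on-treatment results are assigned to visits by analysis window.

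An optional addition applies if the window is wide. Section 6.2.5.2 asks subjects with a Week 48 value ≥50 to return for a retest within 4 weeks (336 + 28 = day 364). That is inside ±6 weeks and outside ±6 days, so the last-available rule could replace a failure with a later success. The retest is clearly on-treatment only for about 8 days (the 7-day supply plus the 1-day cut-off), unless prescribed drug counts as study drug. Reporting how many subjects were reclassified this way would make the effect visible.

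The cost is wording in the affected sections and one programming rule, with no extra visits or subjects. Under a wider window the Week 48 results come from a broader range of days. The reported failure proportion could rise slightly because results are kept, or fall where a retest replaces a failure.

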6.2.5.1 Management of Viral Rebound

Subjects who meet either of the criteria listed below will be considered to have virologic rebound:

- At any post Day 1 Visit, an HIV-1 RNA ≥ 50 copies/mL which is subsequently confirmed at the following visit (scheduled or unscheduled)
- Any subject with HIV-1 RNA ≥ 50 copies/mL at study drug discontinuation

Following the unconfirmed virologic rebound, subjects will be asked to return to the clinic for a blood draw, 4 weeks after the date of the original test that had an RNA ≥50 copies/mL. If virologic rebound is confirmed

[figure not shown]
and the HIV-1 RNA is \geq 200 copies/mL, the blood sample from the confirmation visit will be the primary sample used for HIV-1 genotypic and phenotypic testing. After a subject's first post-baseline resistance test, additional testing will be conducted on a case-by-case basis. Any subject may be discontinued at Investigator's discretion or per local treatment guidelines.

If no resistance is detected from the genotype or phenotype, the subject may remain on study drug and HIV-1 RNA test should be again repeated 2-3 weeks later. If HIV-1 RNA \geq 50 copies/mL remains Investigators should carefully evaluate the risks and benefits of remaining on study drug and document this assessment in the on-site medical record.

Subjects who are nonadherent on an ongoing basis will be considered for discontinuation per the Investigator's discretion or local treatment guidelines. Sub-investigators who opt to discontinue study drugs for an individual subject must discuss with the Investigator prior to study drug discontinuation.

For subjects who are off study drug but remain in study, it will be the Investigator's discretion to manage virologic rebound.

Figure 1

6.2.5.2 Subjects with HIV-1 RNA ≥ 50 copies/mL at Study Drug Discontinuation or Week 48

Subjects with HIV-1 RNA \geq 50 copies/mL at Study Drug Discontinuation, last Visit, or Week 48 will be considered virologic failures. Subjects with HIV-1 RNA \geq 50 copies/mL at Week 48 will be asked to return for an unscheduled visit within 4 weeks for a retest as detailed in Section 6.2.5. Subjects with HIV-1 RNA \geq 200 copies/mL will also have resistance testing as detailed in Section 6.2.5.

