7.3 Adverse Events and Serious Adverse Events

7.3.1 Adverse Events

Following initiation of study medication, all AEs regardless of cause or relationship until end of study must be reported to the study database.

All AEs should be followed up until resolution/return to baseline or until the adverse event is stable, if possible.

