8.6.3 Laboratory Evaluations

Selected laboratory data (using conventional units) will be summarized using only observed data. Absolute values and changes from baseline at all scheduled visits will be summarized.

Graded laboratory abnormalities will be defined using the Grading of Laboratory Abnormalities in Appendix 2

Incidence of treatment-emergent laboratory abnormalities, defined as values that increase at least 1 toxicity grade from baseline at any time post baseline up to and including the date of last dose of study drug plus 30 days will be summarized. If baseline data are missing, then any graded abnormality (i.e., at least a Grade1) will be considered treatment emergent. The maximum post baseline toxicity grade will be summarized by laboratory parameter.

Laboratory abnormalities that occur before the first dose of study drug or after the last dose of study drug plus 30 days will be included in a data listing.

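### Section 6.2.2.3 records an out-of-window visit as missing and nothing says the results are kept by actual date, which conflicts with the snapshot, safety and adverse-event sections

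*Combined protocol and SAP*

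**What the plan says.** Section 6.2.2.3 sets the visit windows: "Study visits are to be completed within ± 2 days of the protocol specified visit date (based on the Day 1 visit) through Week 12", and "visits for Week 12, 24, 36 and 48 should be completed ± 6 days of the protocol specified date". It then gives the consequence of missing a window: "If the subject is not evaluated within the visit window, the database will reflect missing/no available data for that visit". The procedures it lists for each visit include "Review/record of SAE/AE's and changes in concomitant medications" and the blood samples of Section 6.2.4.1, which cover HIV-1 RNA, chemistry, hematology and CD4 count.

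The sections that use these data set no matching limit:

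- **Section 8.5.1.1** opens with "All HIV-1 RNA data collected on-treatment (i.e. including data collected up to 1 day after the last dose date of the study drug"), all of which enters the snapshot. A subject who stops drug for a reason other than lack of efficacy and has no Week 48 result is classified by the last available on-treatment RNA.
- **Sections 8.2.3 and 8.6** include safety data up to 30 days after the last dose.
- **Section 8.6.3** counts treatment-emergent abnormalities "at any time post baseline up to and including the date of last dose of study drug" plus 30 days, and summarizes the maximum grade after baseline.
- **Section 7.3.1** requires that, once study drug has started, "all AEs regardless of cause or relationship until end of study must be reported to the study database".

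Section 8.3 adds that missing visit values are generally not imputed. Section 9.2.8 limits the study file to data required by the schedule.

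**The concern.** The sentence in Section 6.2.2.3 is about what the database holds, not about how a by-visit table is built. If site staff follow it literally, a real viral load or graded laboratory value from a visit a few days late may not be available to analyses that need no nominal visit. The last available RNA, the maximum toxicity grade and adverse-event counts depend only on a result and its date.

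The primary endpoint is a failure proportion in about 100 subjects, and it is likely to rest on few events. One misclassified subject is therefore visible in the result. Agreeing on a single window width would not solve this, because the rule would still apply at whatever width was chosen.

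**Working it through.** The plan gives no figure to reproduce. Section 8.8 states about 100 subjects without a calculation, and Section 8.5.1 calls the primary analysis descriptive. The check is a comparison of sections, one worked case, and an illustration under stated assumptions.

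**1. Is there a rescue clause?** Nothing in Sections 6.2, 8.2, 8.3, 8.5, 8.6 or 9.2.8 says that an out-of-window result is entered under its actual date or as an unscheduled visit. Section 8.5.1.1 refers to a Week 48 analysis window, but Section 8 never defines it.

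**2. Worked case.** Suppose a subject has:

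- RNA below 50 copies/mL at an in-window Week 24 visit;
- RNA of 50 or more at a Week 36 visit held more than 6 days late;
- discontinuation before Week 48 for a reason other than lack of efficacy, with no later qualifying on-treatment RNA.

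| Handling of the late visit | Last available on-treatment RNA | Snapshot category |
|---|---|---|
| Entered by actual date | Week 36, 50 or more | HIV-1 RNA 50 or more (failure) |
| Shown as missing | Week 24, below 50 | No virologic data |

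The early discontinuation visit does not reliably supply the missing value. Section 6.2.2.4 asks for it within 5 days of stopping, while Section 8.5.1.1 accepts RNA only up to 1 day after the last dose. A sample drawn on days 2 to 5 does not count.

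The subject stays in the full analysis set either way, so each such case changes the primary proportion by 1/100 = 1 percentage point. The proportion below 50 does not change in this case, because the subject is not counted there under either handling.

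**3. How many visits could be affected?** The documents give no spread of visit dates. Assume actual dates are normal around the target with SD s days. Counting whole days, a visit is outside ±2 days with probability 2[1 − Φ(2.5/s)] and outside ±6 days with probability 2[1 − Φ(6.5/s)]. Weeks 4 and 8 use ±2 days; Weeks 24 and 36 use ±6 days. Week 12 is left out because Section 6.2.2.3 places it under both widths. Week 48 is left out because the Appendix 1 footnote that appears to belong to it gives ±6 weeks.

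Expected out-of-window visits per subject, of four = 2 × P(outside ±2) + 2 × P(outside ±6).

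| Assumed s (days) | Outside ±2 days | Outside ±6 days | Expected of 4 visits |
|---|---|---|---|
| 2 | 21% | 0.1% | 0.42 |
| 3 | 40% | 3% | 0.87 |
| 5 | 62% | 19% | 1.62 |
| 7 | 72% | 35% | 2.15 |

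Weeks 4 and 8 supply nearly all of the total at s = 2, about 0.81 of 0.87 at s = 3, and 1.44 of 2.15 at s = 7. The only listed endpoint at those two visits is the Week 4 patient-reported outcome. The table shows how often the rule would be triggered. It does not show how many failures or high-grade laboratory values would be lost.

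**The case against.** The best defence is that the words limiting the rule to the visit concerned may mean only that the nominal slot (Week 4, Week 8 and so on) stays blank in by-visit tables. Section 7.3.1 on adverse events, Section 8.6.3 on laboratory grades and Section 9.2.7 on complete case histories can be read as confirming that nothing is discarded. That reading is possible, and it rules out a flat statement that data are erased. It does not settle the matter, because the sentence names the database and no section says where the late result goes.

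Four stronger readings are tempting, and the documents do not support them:

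- **Adverse events would be lost.** Section 7.3.1 independently requires them in the database. This is a conflict to resolve, not a settled loss.
- **A late visit could not confirm rebound.** Section 6.2.5.1 accepts a value "which is subsequently confirmed at the following visit (scheduled or unscheduled") and sets its own retest at 4 weeks, to which no window is attached. Rebound is also not an analysis in Section 8. If done on drug, that retest can supply a later RNA value and so prevent the worked case.
- **All results would otherwise be used.** For subjects still on drug, the snapshot is tied by design to a Week 48 window, so some exclusion by date is intended.
- **The rule favours the drug.** Nothing in the documents shows that late attenders are less adherent. Blanked Week 48 results also lower the proportion below 50. Assume 100 subjects, 2% truly at 50 or more, 10% of Week 48 results blanked independently of outcome, and all of them otherwise usable. Expected failures fall from 2.0 to 100 × 0.02 × 0.90 = 1.8, while subjects counted below 50 fall from 98 to 100 × 0.98 × 0.90 = 88.2. The first change flatters the drug and the second, larger one does not.

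**Conclusion.** The point holds as an unresolved conflict between a data-entry rule and the analyses that depend on the data. Section 6.2.2.3, read as written, cannot be followed together with Sections 7.3.1, 8.2.3, 8.5.1.1, 8.6 and 8.6.3. It can move a viremic early stopper out of the failure category at 1 percentage point per subject, and it can remove graded laboratory values from the safety summaries.

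The per-subject shift rests only on the stated sample size of about 100. The range of 0.4 to 2.2 visits out of window rests on an assumed normal spread with SD 2 to 7 days. The number of reclassified subjects and the net direction of bias cannot be derived from the documents. The conflict itself depends on none of these assumptions.

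**What to change.** Replace the sentence in Section 6.2.2.3 with: *A visit outside the window is a protocol deviation; all data are entered with the actual date.*

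In Section 8, state that last-available RNA, adverse events, and treatment-emergent and maximum laboratory grades use all results by actual date. Define analysis windows there for the by-visit summaries and for the Week 48 snapshot. While doing so, reconcile the visit windows in Section 6.2.2.3 with those in Appendix 1.

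The cost is one replaced sentence, a short set of window definitions, and slightly more spread-out dates in by-visit tables. No treatment or visit procedure changes.
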